8.1 Extent of Exposure

For any investigational medicinal product (IMP) or non-IMP (NIMP), duration of treatment (days) is defined as the number of days from first exposure to the day of last exposure (both inclusive).

8.1.1 IMP (Gonadotropins)

Exposure to gonadotropins will be summarized as the duration of stimulation, the total dose - both the actual total dose administered and the intended total dose (i.e. the sum of the dialed doses recorded by the subject), and the average daily dose defined as the total dose divided by the number of stimulation days. Frequency tables will be included to describe the duration of treatment by categories (<7, 7-8, 9-10, 11-12 and \geq 13 days). The number of stimulation days will also be tabulated by treatment group.

Investigator-requested decreases and increases of the gonadotropin dose will be captured during the stimulation period. The requested dose change (decrease / increase / no change) on stimulation day 5 will be tabulated. Furthermore, the total number of dose increase requests and dose decrease requests per subject will be tabulated.

In addition, summaries of the total dose administered from day 5 to last stimulation day, the maximum and minimum daily doses, the final planned/administered dose, will be presented.

These summary tables will be produced for all subjects who started stimulation, and for subjects who completed the stimulation cycle, i.e. underwent triggering of final follicular maturation. The summaries for subjects who completed the stimulation cycle will also be produced by the triggering drug (i.e., hCG or GnRH agonist).

8.1.2 NIMPs in the Fresh Cycle

GnRH Antagonist

Exposure to GnRH antagonist will be summarised as the total dose administered (mg) and duration of treatment (days). In addition, the summary of the starting day of the GnRH antagonist will be presented. This table will be produced overall and for subjects that completed stimulation, i.e. underwent triggering of final follicular maturation.

Drug for Triggering of Final Follicular Maturation

For subjects who underwent triggering of final follicular maturation, the following information will be summarized: triggering criterion met (yes/no) and the drug used for triggering (hCG or GnRH agonist).

Luteal Phase Support

For subjects who initiated luteal phase support with progesterone, the following information will be summarized: total dose administered (mg) and duration of treatment (days).

8.1.3 NIMPs in the Cryopreserved Cycles

In the programmed cryopreserved cycles, exposure to estradiol will be summarized by cycle as the total dose administered (mg) and duration of treatment (days), and exposure to IM progesterone will be summarized by cycle as the total dose administered (mg) and duration of treatment (days).

In the natural cryopreserved cycles, exposure to vaginal progesterone will be summarized by cycle as the total dose administered (mg) and duration of treatment (days).

8.2 Treatment Compliance

Non-compliance to IMP is expected to be limited and will be presented in listings. Similarly, listings will be prepared for subjects with deviations in the NIMP schedules for the fresh and cryopreserved cycles, such as

- GnRH antagonist in the fresh cycle not administered according to protocol
- hCG or GnRH agonist in the fresh cycle not administered according to protocol
- Progesterone in the fresh cycle or cryopreserved cycles not administered according to protocol
- Estradiol in the cryopreserved cycles (programmed) not administered according to protocol

9 Efficacy

9.1 General Considerations

9.1.1 Primary Endpoint and Secondary Efficacy Endpoints

The primary efficacy endpoint, cumulative ongoing pregnancy rate, will be compared formally between the two treatment groups. The cumulative live birth rate derived from post-trial follow-up assessments will be tested formally as a key secondary efficacy endpoint (see Section 11.1.2).

A hierarchical testing procedure is used to control the overall type 1 error rate. Upon achieving statistical significance about the primary endpoint at the 0.05 alpha level, the cumulative live birth rate will be formally tested at the 0.05 alpha level for inferential conclusions (see Section 11.1.2).

The secondary endpoints related to pregnancy and implantation parameters are considered supportive of the primary endpoint (cumulative ongoing pregnancy rate). The secondary efficacy endpoints related to ovarian response and embryo development parameters are intended to provide additional characterization of FE 999049.

9.2 Analysis and Presentation of Primary and Secondary Efficacy Endpoints

Summary tables and treatment comparisons for the primary endpoint will be presented for both the mITT and PP analysis sets. In case that the mITT and ITT analysis sets are not identical (i.e. at least one subject is randomized but not exposed) the summary tables and treatment comparisons will also be presented for the ITT analysis set. As applicable for the secondary endpoints, summary tables and treatment comparisons may be presented for the mITT and PP analysis sets.

All tabulations will be presented by treatment group. Continuous variables will be presented with number of subjects, mean, standard deviation, median, inter-quartile range, minimum, and maximum. Categorical variables will be presented with number and percentage of subjects within each specific category.

All statistical tests will be performed using a two-sided test at a 5% significance level. Treatment differences will (where appropriate) be presented with 95% confidence intervals and p-values corresponding to the statistical test of the hypothesis of 'equal effect' against the alternative of 'different effect'.

Visual displays will be produced as appropriate. All primary and secondary efficacy endpoints will be listed. Listings will only be produced for the mITT.

9.2.1 Multiplicity

In order to handle the formal testing procedures for the primary endpoint of cumulative ongoing pregnancy rate and the key post-trial endpoint of cumulative live birth rate, the overall type-I error will

be controlled by the use of a hierarchical inferential approach. Statistical significance of the primary endpoint at the 0.05 alpha level is required before drawing inferential conclusions about the key post-trial endpoint of the cumulative live birth rate. This fixed hierarchical approach will ensure a strong control of the overall type-I error rate at the 0.05 level.

All additional analyses of the primary endpoint and secondary efficacy endpoints are considered as supportive. Adjustments for multiplicity will therefore not be applied.

9.2.2 Missing Data

Missing observations for the primary endpoint of cumulative ongoing pregnancy rate will be imputed as 'negative' irrespective of the reason why data are not recorded. Similarly, for other pregnancy endpoints (β hCG, clinical pregnancy and vital pregnancy) missing data will be imputed as 'negative' with the exception of a later observation in that cycle confirming that an earlier missing observation was in fact 'positive', e.g. in case of a missing β hCG test result and a confirmed clinical pregnancy in the same cycle then the β hCG test result will be imputed as 'positive'.

However, if a subject eligible for additional transfer chooses not to come back within the one-year period from the start of stimulation due to miscellaneous personal reasons, this is not considered a censored or missing observation due to loss to follow-up for cumulative pregnancy endpoints. Rather, the observed one-year cumulative pregnancy outcomes reflect the subject's real-life decision or circumstance.

The COVID-19 pandemic induced a trial hold where new cryopreserved cycles were not allowed to be initiated. The primary endpoint analysis is based on cryopreserved cycles initiated within 12 calendar months from the date of randomization (subsequently referred to as 12 calendar months). However, for a subset of subjects, part of their 12 calendar months will have been lost due to the COVID-19 pandemic trial hold. Therefore, the pandemic could induce missing primary endpoint information. Based on the approach outlined above, these primary endpoint assessments will be imputed as 'negative'. In order to assess the impact, if any, of the COVID-19 pandemic on the primary endpoint, additional sensitivity analyses are planned. As part of one of these additional sensitivity analyses, the primary endpoint analysis will be repeated, but with the application of multiple imputation for those endpoints missing specifically due to the pandemic.

When applying the method of multiple imputation, three types of missingness are used: 1) missing the primary endpoint assessment from a recorded cryopreserved cycle because of the COVID-19 pandemic, 2) missing the primary endpoint assessment from a cryopreserved cycle that would have theoretically occurred had it not been for the COVID-19 pandemic, and 3) missing the primary endpoint assessment because of any other reason. The method of multiple imputation will only be applied to those endpoints that are missing because of the first two types of missingness. Missing endpoints because of the third type of missingness will continue to be imputed as 'negative'. If a

subject was still in the trial at the start of the COVID-19 pandemic trial hold and initiates an additional cryopreserved cycle after the end of the trial hold, but within 12 calendar months from their date of randomization, then this subject's endpoint will be considered non-missing and will not be imputed using multiple imputation.

Multiple imputation will be based on a risk-stratified hot deck imputation strategy. Subjects that are to receive imputation will be stratified by assigned treatment arm and the number of previous transfers within the study. The subjects not receiving imputation will form an imputation pool. The imputation pool will also be stratified by assigned treatment arm and the number of previous transfers within the study. If a stratum within the imputation pool contains fewer than 10 subjects, strata may be collapsed to increase the membership of a particular stratum. For each subject receiving imputation, the imputation pool will be further reduced to those subjects that have an endpoint assessment that occurred at or beyond the first date of missingness for the imputed subject's primary endpoint. Hot deck replacement commences from the reduced, stratified imputation pool 10 times, forming 10 analysis datasets from which combined estimates will be obtained using the method described by Rubin.⁵

For subjects with transfer but missing observations on the number of viable fetuses 8-9 weeks after transfer the number of viable fetuses will be imputed as zero irrespective of why data is not recorded. For subjects with transfer but missing information on the number of gestational sacs 5-6 weeks after transfer, the number of gestational sacs will be imputed as the number of viable fetuses 8-9 weeks after transfer.

For subjects with cycle cancellation prior to triggering of final follicular maturation, the numbers of oocytes retrieved, metaphase II oocytes, fertilized oocytes, and blastocysts on day 5 will be imputed as zero.

Missing values will not be imputed for any of the other secondary endpoints, unless otherwise noted.

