Recruitment to the trial has been completed and all fresh cycles have been completed up to the ongoing pregnancy visit. The current activities are cryopreserved cycles initiated within 12 months from the start of controlled ovarian stimulation as well as pregnancy follow-up to birth, 4 weeks and 1 year after birth in the fresh and cryopreserved cycles.

Ferring is issuing guidance for continued trial conduct and management of subjects included in the trial. The table below provides guidance for how to manage the subjects according to stage in the trial.

Continued trial conduct for management of subjects included in the trial

- Cryopreserved cycles:
 - Cycles not yet initiated: do not initiate until this COVID-19 related temporary deferral of cryopreserved cycles has been lifted
 - Cycles already initiated and where transfer has not occurred: continue per protocol and document any deviations
 - Cycles where transfer has occurred: continue per protocol and document any deviations
 - Note: timelines for cryopreserved cycles will be extended by the approximate duration
 of the temporary deferral of cryopreserved cycles required by this change to the
 protocol
- Pregnancy follow-up: continue per protocol and document any deviations

In case subjects are prevented from attending scheduled visits, the investigator (or designee) will attempt to contact the subject by phone or other ways to inquire about potential adverse events and changes to concomitant medication.

Page 4 of 4

IMPLICATIONS OF CHANGE:

The implications of these changes to the protocol are summarized below. The actions are considered urgent safety measures due to COVID-19 required to protect subjects against immediate hazard to their health and safety and are therefore implemented immediately.

- Trial sites, regulatory authorities and independent research boards will be informed.
- Subjects will be verbally informed by the investigator of potential changes to the course of
 action, as applicable for the individual subject. This will be documented in the subject's
 medical records.
- Protocol deviations (including deviations to the aspects described in this 'change to
 protocol') should be avoided whenever possible except where necessary to eliminate an
 immediate hazard to the subject. If deviations occur they will be documented as per
 standard practice, with additional specification whether they were related to the COVID-19
 situation.

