2.2 Endpoints

Primary Endpoint

• Cumulative ongoing pregnancy rate (at least one intrauterine viable fetus 8-9 weeks after transfer) after the fresh cycle and cryopreserved cycles initiated within 12 months from the start of controlled ovarian stimulation

Secondary Endpoints

- Ongoing pregnancy rate (at least one intrauterine viable fetus 8-9 weeks after transfer) in the fresh cycle and in the cryopreserved cycles
- Time from start of controlled ovarian stimulation to ongoing pregnancy across the fresh and cryopreserved cycles, including duration and number of cycles before achieving ongoing pregnancy
- Ongoing implantation rate (number of intrauterine viable fetuses 8-9 weeks after transfer divided by number of blastocysts transferred) in the fresh cycle, the cryopreserved cycles and cumulatively
- Clinical pregnancy rate (at least one gestational sac 5-6 weeks after transfer) in the fresh cycle, the cryopreserved cycles and cumulatively
- Vital pregnancy rate (at least one intrauterine gestational sac with fetal heart beat 5-6 weeks after transfer) in the fresh cycle, the cryopreserved cycles and cumulatively
- Implantation rate (number of gestational sacs 5-6 weeks after transfer divided by number of blastocysts transferred) in the fresh cycle, the cryopreserved cycles and cumulatively
- Positive βhCG rate (positive serum βhCG test 10-14 days after transfer) in the fresh cycle, the cryopreserved cycles and cumulatively
- Proportion of subjects in the fresh cycle with triggering of final follicular maturation (with hCG, with GnRH agonist, and in total), cycle cancellation and transfer cancellation
- Number and size of follicles on stimulation day 5 and end-of-stimulation
- Number of oocytes retrieved and proportion of subjects with <4, 4-7, 8-14, 15-19 and ≥20 oocytes retrieved
- Number and percentage of metaphase II oocytes (only applicable for those inseminated using ICSI), number of fertilized oocytes, fertilization rate as well as number and quality of blastocysts on day 5 after oocyte retrieval
- Endometrial thickness and echogenicity pattern on stimulation day 5 and end-of-stimulation
- Oocyte utilization rate (number of blastocysts transferred or cryopreserved divided by the number of oocytes retrieved) and oocyte efficiency index (cumulative number of ongoing pregnancies per oocyte retrieved)
- Number and percentage of blastocysts surviving cryopreservation and number and percentage of blastocysts with re-expansion after cryopreservation

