9.3.2 Sensitivity Analyses

The primary analysis will be repeated for the subjects in the PP analysis set as sensitivity analysis, as well as in the ITT analysis set if the ITT analysis set differs from the mITT analysis set. The outcomes of these analyses are considered supportive.

The primary analyses described above will be repeated restricted to subjects with oocytes retrieved and to subjects undergoing blastocyst transfer, as applicable.

Missing data for the primary endpoint is expected to be limited due to the trial design, but may occur if the subject is lost to follow-up before ongoing pregnancy is assessed. If one or more such subjects have a positive pregnancy test result (β hCG test, clinical pregnancy or vital pregnancy) prior to loss to follow-up, the impact of imputing the ongoing pregnancy will be investigated in a sensitivity analysis.

It is also possible that a subject without pregnancy assessments following a transfer has her birth/miscarriage/elective termination outcome available at a later time. The information may be evaluated to help determine the ongoing pregnancy status in the sensitivity analysis on a case-by-case basis.

In order to assess the impact, if any, of the COVID-19 pandemic on the primary endpoint, additional sensitivity analyses are planned which will assess both the timing of the COVID-19 pandemic trial hold and the imputation method applied to missing data that arises due to the pandemic. The primary endpoint analysis is based on cryopreserved cycles initiated within 12 calendar months from the date of randomization (subsequently referred to as 12 calendar months). However, for a subset of subjects, part of their 12 calendar months will have been lost due to the COVID-19 pandemic trial hold. These subjects will be allowed to initiate cryopreserved cycles within 12 months of active study days (subsequently referred to as 12 study months). Because the last randomization occurred on 17 September 2019 and the trial hold began subsequent to the issuing of Protocol Amendment 01 on 19 March 2020, the first COVID-19 pandemic sensitivity analysis will repeat the same methodology as the primary endpoint analysis (i.e.; same analysis set, same inference method, and same imputation method), but will instead use the cumulative ongoing pregnancy rate from cycles initiated within the

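### A woman with a missed 8-9 week scan but a documented birth is scored not pregnant in the primary analysis; the later-observation rule should cover the primary endpoint

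*SAP*

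**What the plan says.** The primary endpoint (SAP 2.2) is: "Cumulative ongoing pregnancy rate (at least one intrauterine viable fetus 8-9 weeks after transfer) after the fresh cycle and cryopreserved cycles initiated within 12" (the period is in months, counted from the start of stimulation).

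SAP 9.2.2 states that missing observations for this endpoint "will be imputed as 'negative' irrespective of the reason why data are not recorded". Protocol 9.7.1 has the same rule. For βhCG, clinical and vital pregnancy, missing results are also negative, but "with the exception of a later observation in that cycle confirming that an earlier missing observation was in fact 'positive". That exception is not given to ongoing pregnancy.

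Data lost to the pandemic follow the same rule in the primary analysis: "Based on the approach outlined above, these primary endpoint assessments will be imputed as 'negative". Multiple imputation enters elsewhere: "As part of one of these additional sensitivity analyses, the primary endpoint analysis will be repeated, but with the application of multiple imputation". SAP 9.3.2 lists this as the third COVID-19 sensitivity analysis. Its first type of missingness is "missing the primary endpoint assessment from a recorded cryopreserved cycle because of the COVID-19 pandemic". The value is drawn from women in the same arm with the same number of previous transfers, restricted to those assessed at or beyond the first missing date.

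SAP 9.3.2 also accepts that a woman without pregnancy assessments after a transfer may later have a known birth, miscarriage or elective termination. That information may be evaluated to "help determine the ongoing pregnancy status in the sensitivity analysis on a case-by-case basis".

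Cumulative live birth is tested next in the hierarchy (SAP 11.1.1). There, only women with no live-birth information default to negative.

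**The concern.** In practice, a live birth from a transfer shows that a viable intrauterine fetus was present 8-9 weeks after it, which is the event the primary endpoint counts. Scoring that woman negative therefore replaces a known value with a wrong one, and it does so on the main endpoint while the supportive pregnancy endpoints are protected. It also lets one transfer be a failure in the primary endpoint and a success in the endpoint tested directly after it.

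The only route back is optional. The SAP gives no criterion for what counts as proof, names no one to decide, and does not require the decision to be taken blinded. With 50 placebo women, single records carry weight, so unwritten handling is a weak point.

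The hot-deck analysis has a related gap. Imputation is meant for values that are unknown, yet nothing in the text removes from the draw a woman whose outcome from the recorded cycle is documented.

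**Working it through.** **1. The plan's own figure.** Inputs from SAP 3.2: 500 and 50 women, 30% against at most 3%. Unpooled standard error = √(0.30×0.70/500 + 0.03×0.97/50) = √(0.000420 + 0.000582) = 0.0317. Then 0.27/0.0317 = 8.5, and 8.5 − 1.96 is about 6.6, so power exceeds 99.99%. Exact enumeration of the planned rule (Wald interval, or one-sided Fisher with fewer than 5 placebo pregnancies) also exceeds 99.99%, with Fisher taken at 0.025 or at 0.05 because SAP 9.3.1 does not state its level. For live birth, 27% against 3%, the result is 99.99%. The stated 99% or more reproduces for both.

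**2. Tracing one woman.** She has a transfer, misses the 8-9 week scan, and a birth from that transfer is documented by database lock.
- Primary endpoint (SAP 9.2.2): negative.
- Sensitivity analysis (SAP 9.3.2): possibly positive, if someone chooses to evaluate the record.
- Third COVID-19 sensitivity analysis, if the scan was missed because of the pandemic: ten draws from donors.
- Cumulative live birth (SAP 11.1.1): positive.

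If the record instead shows a loss before 8-9 weeks, the primary score of negative is correct. Only a draw could then contradict it.

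**3. Size in the FE 999049 arm.** The documents give no count of such women, so *m* is an assumption. Base case: 150/500 against 2/50. The 95% limits are d ± 1.96√(p₁(1−p₁)/500 + p₀(1−p₀)/50).

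| True FE 999049 pregnancies scored negative (*m*) | FE 999049 rate | Difference (points) | 95% limits |
|---|---|---|---|
| 0 | 30.0% | 26.0 | 19.2 to 32.8 |
| 1 | 29.8% | 25.8 | 19.0 to 32.6 |
| 5 | 29.0% | 25.0 | 18.3 to 31.7 |
| 10 | 28.0% | 24.0 | 17.3 to 30.7 |
| 25 | 25.0% | 21.0 | 14.4 to 27.6 |

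Each case costs 1/500 = 0.2 points. With 2 placebo pregnancies the planned test is Fisher's; its one-sided p is 0.00001 at *m* = 0 and 0.00015 at *m* = 25.

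**4. Size in the placebo arm.** Each case is 1/50 = 2 points, in the other direction. Starting from 150/500 against 2/50, counting 1, 2 or 3 further placebo births gives differences of 24.0, 22.0 and 20.0 points. One-sided Fisher p is 0.00006, 0.0003 and 0.0012. At 5 placebo pregnancies the plan switches to the Wald interval, here 10.8 to 29.2 points. Scoring such births negative would flatter FE 999049.

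**5. Power.** If 5%, 10% or 20% of true FE 999049 pregnancies were scored negative, the arm's rate would be 28.5%, 27% or 24%. Power under the planned rule would be 99.996%, 99.99% and 99.85%.

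**6. The draw.** If the donors' success rate is *p*, a woman with a known birth is drawn negative with probability 1 − *p*, and a woman with a known early loss is drawn positive with probability *p*. Either contradicts the record for any *p* strictly between 0 and 1. The documents do not give *p*.

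**The case against.** The other side has several good points.

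The existing exception works within a cycle, and the ongoing-pregnancy visit is the last scheduled visit of a cycle (Protocol 6.1.12, 6.2.1.7, 6.2.2.8). No later scheduled in-cycle result exists to fill from. This explains the wording, but SAP 9.3.2 shows that the authors knew later information could exist.

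Counting missing as failure is prespecified and conservative when errors fall in the active arm, where most transfers are expected. That stands, except that a placebo case works the other way.

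Cases should be rare. Birth follow-up is systematic only after a confirmed ongoing pregnancy (Protocol 6.3), so a birth after a missed scan would be learned incidentally. Amendment 01 reports all fresh cycles complete up to the ongoing-pregnancy visit. It does say "In case subjects are prevented from attending scheduled visits, the investigator (or designee) will attempt to contact the subject by phone" or by other means, but the stated purpose is adverse events and concomitant medication, not births. Losses could surface this way, since Protocol 8.3.2 has them reported as adverse events. All of this stands.

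A woman without a vital pregnancy at 5-6 weeks goes to end-of-cycle assessments, and SAP 4 separates anticipated from pandemic missingness. A documented early loss may therefore never enter the draw. That is a fair reading, but SAP 9.2.2 does not say so.

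Using births known by database lock makes ascertainment depend on calendar time, because births are reported in later addendums (Protocol 13.1). This is a true cost of the repair.

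**Conclusion.** The point holds as a gap in a scoring rule. In the primary analysis a missed 8-9 week assessment is negative even when a birth from that transfer is documented, and the only remedy is discretionary and confined to a sensitivity analysis. In the third COVID-19 sensitivity analysis, the draw lacks an exception for known outcomes. The effect is 0.2 points per FE 999049 case and 2 points per placebo case, with few cases expected. The base case assumes the design rates and 2 placebo pregnancies.

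A reader might infer more, but the documents do not support it:
- The draw does not touch the primary analysis, where pandemic-related gaps are also negative.
- A loss before 8-9 weeks does not contradict the primary score; it agrees with it.
- The SAP did not overlook later outcomes; it foresaw them without writing a rule.
- No particular total bias can be stated, since no number of cases is given. Nor can the planned 30% serve as the donor rate: it is a cumulative rate over all treated women, while donors are matched on transfers and assessment date.
- Neither power nor the significance conclusion is at risk at the design rates.

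**What to change.** Before unblinding, amend SAP 9.2.2 and 9.3.2 as follows.

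- **Primary endpoint.** If the 8-9 week assessment is missing, score positive when a delivery from that transfer, or a later scan showing a viable intrauterine fetus from it, is documented by database lock. All other missing assessments stay negative.
- **Hot-deck analysis.** Take out of type 1 imputation any woman with a documented birth, later viable fetus, or loss before the 8-9 week window, and use the known value.
- **Process.** Replace the case-by-case sentence in SAP 9.3.2 with this rule, and settle the records at the blinded data review already planned in SAP 5.
- **Sensitivity.** Keep the present all-negative rule as a sensitivity analysis, so that the effect of the change is visible.

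The cost is SAP wording and a check of a few records; no new visit or data collection is needed. The downside is that outcomes learned after database lock still follow the negative rule. Ascertainment then depends somewhat on when a woman was treated, although not by design on her arm.
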